4. STUDY POPULATION

4.1. Inclusion Criteria

1. Be able to understand and be willing to sign the written informed consent for the trial. A signed informed consent form must be appropriately obtained prior to the conduct of any trial-specific procedure.
2. Be ≥ 18 years of age on day of signing informed consent.
3. Histologically confirmed cancer of the pancreas (KRAS mutated) with metastases and progression on at least ≥ 2 prior treatment regimens for their disease.
4. Known mutation status of KRAS and BRAF kinases. For those patients in which this has not previously been determined, the patient must have an archival tumor specimen (primary or metastatic stie) available to submit to confirm KRAS and BRAF status.
5. Have a performance status of 0 or 1 on the ECOG performance scale.
6. Demonstrate adequate organ function as defined below:
 - a. Absolute neutrophil count $\geq 1,500/\text{mm}^3$
 - b. Platelet concentration $\geq 60 \times 10^9/\text{L}$

- c. Hemoglobin ≥ 8.5 g/dL. Criteria must be met without erythropoietin dependency and without packed red blood cells (pRBC) transfusion within the last 2 weeks.
- d. Serum creatinine $< 1.5 \times$ institutional ULN.
- e. Total bilirubin ≤ 2.5 mg/dL
- f. Alanine aminotransferase (ALT) and Aspartate aminotransferase (AST) $< 5 \times$ ULN
- g. Prothrombin time (PT) ≤ 60 seconds or International Normalized Ratio (INR) ≤ 2.3
- 7. Female participants of childbearing potential must have a negative serum pregnancy test performed within 24 hours prior to receiving first dose of trial medication. Post-menopausal women (defined as no menses for at least 1 year) and surgically sterilized women are not required to undergo a pregnancy test.
- 8. A female participant is eligible to participate if she is not pregnant, not breastfeeding, and at least one of the following conditions applies:
 - a. Not a woman of childbearing potential (WOCBP)
 - OR
 - b. A WOCBP who agrees to follow the contraceptive guidance during the treatment period and for at least 30 days after the last dose of trial treatment.
- 9. Male participants must agree to use contraception during the treatment period and for at least 30 days after the last dose of trial treatment and refrain from donating sperm during this period.
- 10. Patient must have QTC of ≤ 500 ms.
- 11. Subject must be able to swallow and retain oral medication.
- 12. **Measurable disease per RECIST 1.1**

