5. STUDY TREATMENT

5.1. Treatment Dosage and Administration

The specific study drugs, formulation, dosage, administration, and schedule are detailed in Tables 1 and 2 and the sections that follow. Study treatment will be administered on an outpatient basis. Each treatment cycle will be 4 weeks (28 days in duration).

The commercial product for each study drug will be supplied for this trial. Vemurafenib will be provided by Genentech, and Sofarafenib will be provided by Bayer. Refer to Section 9 for Drug Treatment Information and link to prescribing information (package inserts).

Table 1: Study Drugs

Agent	Formulation	Dose	Route	Schedule	Cycle Length
Vemurafenib	240 mg tablets	480 mg	PO	BID	28 days
Sorafenib	200 mg tablets	200 mg	PO	BID	28 days

Table 2: Study Drug Dose Levels

	Vemurafenib	Sorafenib
Dose level 1 (starting dose)	480 mg PO BID	200 mg po bid
Dose level -1	240 mg PO BID	200 mg daily

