8.6. Pregnancy

If a female subject becomes pregnant while receiving the study drug or within 30 days after the last dose of study drug, or if the female partner of a male study subject becomes pregnant while the study subject is receiving the study drug or within 30 days after the last dose of study drug, a report should be completed and expeditiously submitted to HRI Drug Safety/Bayer/Genentech. Follow-up to obtain the outcome of the pregnancy should also occur. Abortion, whether accidental, therapeutic, or spontaneous, should always be

classified as serious, and expeditiously reported as an SAE. Similarly, any congenital anomaly/birth defect in a child born to a female subject exposed to the study drug should be reported as an SAE.

For the pregnancy of a study subject's partner, all efforts should be made to obtain similar information on course and outcome, subject to the partner's consent.

Female patients of childbearing potential should be advised to use contraception during the treatment and at least 30 days after the last dose of study treatment. Women must refrain from donating eggs during this same period.

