- Severe dermatological reactions can occur in patients receiving vemurafenib. Patients should be advised to stop taking vemurafenib and to contact their health-care provider for severe dermatologic reactions.
- Vemurafenib can prolong QT interval, which may result in ventricular arrhythmias. Patients should be advised of the importance of monitoring their electrolytes and the electrical activity of the heart (via and ECG) during treatment with vemurafenib.
- Liver injury leading to functional hepatic impairment, including coagulopathy or other organ dysfunction, can occur with vemurafenib. Patients should be advised of the importance of laboratory monitoring of their liver during treatment with vemurafenib and to contact their health-care provider for relevant symptoms.
- Vemurafenib can cause mild to severe photosensitivity. Patients should be advised to avoid sun exposure, wear protective clothing, use a broad-spectrum UVA/UVB sunscreen and lip balm (SPF≥30) when outdoors to help protect against sunburn.
- Ophthalmologic reactions can occur in patients treated with vemurafenib. Patients should be advised to contact their health care provider immediately for ophthalmologic symptoms.

- Due to potential risk to a fetus woman of child-bearing potential must use effective contraception during treatment with vemurafenib and for 2 weeks after their last dose.
- If a female patient confirms or suspects pregnancy during the study, they should contact their healthcare provider immediately. Any confirmed pregnancy is to be reported within 24 hours as per Section 8.6.
- If a male patient's sexual partner becomes pregnant during the study, they should contact their healthcare provider immediately. Any confirmed pregnancy is to be reported within 24 hours as per Section 8.6.
- Female patients should be advised not to breastfeed during treatment with vemurafenib and for 2 weeks following the final dose.
- Radiation sensitization and recall can occur in patients treated with radiation prior to, during, or after treatment with vemurafenib. Patients should be advised to inform their health care provider if they have had or are planning to receive radiation therapy. Radiotherapy may be allowed while the patient is enrolled in this study if given to help palliate a specific symptom (e.g. bone pain, brain metastases, etc.

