- Patients should be advised of the possible occurrence of hand-foot skin reaction and rash during sorafenib treatments and the measures they should take.
- Patients should be advised that cases of gastrointestinal perforation have been reported in patients taking sorafenib.
- Patients should be informed that temporary interruption of sorafenib is recommended in patients undergoing major surgical procedures due to potential wound healing complications.
- Sorafenib can cause hepatitis which may result in hepatic failure and death. Patients should be advised that liver function tests should be monitored regularly during treatment and that they should report symptoms of hepatitis.

- Due to potential risk to a fetus woman of child-bearing potential must use effective contraception during treatment and for 6 months after the last dose of sorafenib. Male patients with female partners of reproductive potential or who are pregnant must use effective contraception during treatment with sorafenib and for 3 months after receiving their last dose.
- If a female patient confirms or suspects pregnancy during the study, they should contact their healthcare provider immediately.
- Patients on sorafenib should not breastfeed while taking the medication and for 2 weeks after receiving their last dose.
- If a patient misses a dose of sorafenib, the next dose should be taken at the regularly scheduled time; they should not double the dose. Patients should be instructed to contact their healthcare provider immediately if they take too much sorafenib.

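### The 30-day post-treatment contraception minimum for entry is shorter than the 6 months (women) and 3 months (men) that Section 9.2 requires after sorafenib

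*Combined protocol and SAP*

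**What the plan says.** The entry criteria, identical in the synopsis and Section 4.1, set a 30-day minimum after the last dose. Under criterion 8b a woman of childbearing potential is eligible if she "agrees to follow the contraceptive guidance during the treatment period and for at least 30 days after the last dose of trial treatment". Under criterion 9, "Male participants must agree to use contraception during the treatment period and for at least 30 days after the last dose of trial treatment", with no sperm donation over the same period. Section 8.6 says that women of childbearing potential "should be advised to use contraception during the treatment and at least 30 days after the last dose of study treatment" and bars egg donation for that time. It gives no contraception duration for men.

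The patient counselling text in Section 9 gives other intervals, by drug:

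- Vemurafenib (Section 9.1), women of childbearing potential: "must use effective contraception during treatment with vemurafenib and for 2 weeks after their last dose".
- Sorafenib (Section 9.2), women of childbearing potential: "must use effective contraception during treatment and for 6 months after the last dose of sorafenib".
- Sorafenib (Section 9.2), men: "Male patients with female partners of reproductive potential or who are pregnant must use effective contraception during treatment with sorafenib and for 3 months after" the last dose.

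Section 5.1 assigns both drugs to every patient and directs the reader onward: "Refer to Section 9 for Drug Treatment Information and link to prescribing information". Section 5.3 stops both drugs when either is stopped for toxicity.

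**The concern.** Sorafenib is part of the treatment for every patient, so its interval applies to every woman of childbearing potential and to every man in the group that Section 9.2 names. The commitment that decides eligibility is long enough for vemurafenib and too short for sorafenib. Section 8.6, which tells sites what to advise women, carries the same short figure.

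What is at stake is participant and fetal safety. A site that works from the eligibility checklist and Section 8.6 would secure a 30-day commitment and believe the protocol satisfied. The primary endpoint, the two-stage rule, the analysis sets and the sample size do not depend on this point.

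**Working it through.** No statistical figure is involved, so the check is a comparison of the stated durations and simple date arithmetic.

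**Inputs**

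| Group | Source | Interval after last dose |
|---|---|---|
| Women of childbearing potential | Section 9.1 (vemurafenib) | 2 weeks = 14 days |
| Women of childbearing potential | Criterion 8b; Section 8.6 | at least 30 days |
| Women of childbearing potential | Section 9.2 (sorafenib) | 6 months |
| All men | Criterion 9 | at least 30 days |
| Men whose female partner is pregnant or could become so | Section 9.2 (sorafenib) | 3 months |

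**Months in days.** Depending on the start date, 6 calendar months run 181–184 days and 3 calendar months run 89–92 days.

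**Shortfall = sorafenib interval − 30 days**

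- Women: 181 − 30 = 151 to 184 − 30 = 154 days. The 30 days cover 30/184 = 16.3% to 30/181 = 16.6% of the interval.
- Men in the named group: 89 − 30 = 59 to 92 − 30 = 62 days. The 30 days cover 30/92 = 32.6% to 30/89 = 33.7%.
- Average-month check (30.44 days): 6 × 30.44 − 30 = 152.6 days; 3 × 30.44 − 30 = 61.3 days.
- Against vemurafenib: 30 − 14 = 16 days more than Section 9.1 asks of women.

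**Does any text reconcile them?** Criterion 8b refers to contraceptive guidance but does not define it or point to Section 9.2, and it states its own duration. Criterion 9 mentions no guidance. Section 5.1 points to Section 9 for drug information in general, not for the contraception interval. Nothing says that the 9.2 interval overrides the 30 days in 8b, 9 or 8.6.

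**The case against.** The strongest reply is that the texts are compatible. The entry criteria set a floor, Section 9.2 adds a longer duty, and a patient can satisfy both. The undefined guidance in 8b could be read to include Section 9, to which Section 5.1 refers. The 2-week and 6-month intervals do not conflict with each other either: each belongs to its own drug, and a patient taking both must meet the longer.

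Much of this stands. The long interval is in the protocol, Section 9.1 contradicts nothing, and the one real mismatch is the 30-day floor against Section 9.2. But a floor defines who may enter. A patient who agrees to exactly 30 days passes screening and follows the Section 8.6 advice, yet does less than Section 9.2 says she or he must. Compatibility helps only a patient who happens to be told the longer period.

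A second reply is that harm is not shown. What patients are told depends largely on the consent form, which is not in the documents and may already give the longer periods. Section 9.2 is itself counselling text, and Sections 9.1 and 9.2 have patients advised to read the approved labelling. Few patients may be affected: Section 11.2 estimates enrolment of up to 24 and does not say how many fall in these groups. That limits the likely frequency of harm and keeps this a should-fix item. It does not justify leaving two different safety instructions in one protocol.

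**Conclusion.** The concern holds. The post-treatment contraception minimum in criteria 8b and 9, and for women in Section 8.6, is set below the protocol's own requirement for sorafenib. It is about 5 months short for women of childbearing potential and about 2 months short for men whose partner is pregnant or could become so.

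The day counts assume that the last sorafenib dose is also the last dose of trial treatment. Section 5.3 ensures this when treatment stops for toxicity. If a patient's last vemurafenib dose came later than the last sorafenib dose, the shortfall would shrink by that gap. The figures describe duration only; the documents give no basis for sizing the fetal risk. Statistical inference from the trial is unaffected.

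**What to change.** - **Criterion 8b (synopsis and Section 4.1) and Section 8.6:** at least 6 months after the last dose for women of childbearing potential.
- **Criterion 9 (synopsis and Section 4.1):** at least 3 months for men whose female partner is pregnant or could become so. This matches Section 9.2 as written and would allow other men to stay at 30 days. A single 3-month rule for all men is simpler and avoids difficulty if a man's partner status changes or he donates sperm after day 30.
- **One governing sentence:** state that the sorafenib interval in Section 9.2 applies to the combination. Section 9.1 can stay as drug-specific text.
- **Donation limits:** the sperm and egg donation limits are tied to the same periods and would lengthen with them unless the clinical team decides otherwise.
- **Consent form:** correct it if it says 30 days.

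Optionally, extend the Section 8.6 pregnancy-report window, now 30 days after the last dose, and ask about pregnancy at the 3-monthly survival contacts. Section 9.1 ("Any confirmed pregnancy is to be reported within 24 hours as per Section 8.6") covers pregnancies during the study but refers back to Section 8.6, and Section 8.11 asks for all pregnancies without stating a window. Reporting of later pregnancies is thus open to interpretation.

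The cost is a wording amendment and a longer commitment for the patients concerned. Endpoints, statistical design and sample size do not change.

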4.2. Exclusion Criteria

- 1. Is currently participating and receiving trial therapy or has participated in a trial of an investigational agent and received trial therapy or used an investigational device within 2 weeks of the first dose of this trials' treatment.
- 2. Has had prior chemotherapy, targeted small molecule therapy, or radiation therapy within 2 weeks prior to Cycle 1/Day 1 or who has not recovered (i.e. NCI-CTC AE Version 5.0 \leq Grade 1 at the time of signing informed consent) from adverse events due to a previously administered agent(s).

Note: Patients with \leq Grade 2 neuropathy and \leq Grade 2 alopecia are an exception to this criterion and may qualify for the trial.

- 3. Previous BRAF inhibitor use such as vemurafenib, GSK2118436 or sorafenib.
- 4. If patient received major surgery, and has not yet recovered adequately from the toxicity and/or complications from the intervention prior to starting therapy.
- 5. Previously untreated or concurrent cancer that is distinct in primary site or histology from pancreatic cancer except cervical cancer in-situ, treated basal cell carcinoma, or superficial bladder tumor. Subjects surviving a cancer that was curatively treated and without evidence of disease for more than 3 years before

study entry. All cancer treatments must be completed at least 3 years prior to study entry (i.e., signature date of the informed consent form).

6. Has known active central nervous system (CNS) metastases and/or carcinomatous meningitis. Patients with previously treated brain metastases may participate provided they are stable (without evidence of progression by imaging for at least four weeks prior to the first dose of trial treatment and any neurologic symptoms have returned to baseline), have no evidence of new or enlarging brain metastases, and are not using steroids for at least 7 days prior to trial treatment. This exception does not include carcinomatous meningitis, which is excluded regardless of clinical stability.
7. Uncontrolled hypertension (systolic pressure >140 mm Hg or diastolic pressure > 90 mm Hg [NCI-CTCAE v5.0] on repeated measurement) despite optimal medical management.
8. Active of clinically significant cardiac disease including:
 - a. Congestive heart failure New York Heart Association (NYHA) > Class II. (Appendix D)
 - b. Active coronary artery disease (CAD)
 - c. Cardiac arrhythmias requiring anti-arrhythmic therapy other than beta blockers or digoxin.
 - d. Unstable angina (anginal symptoms at rest), new-onset angina within 3 months before randomization, or myocardial infarction within 6 months before randomization.
9. Has history of (non-infectious) pneumonitis that required steroids or current pneumonitis.
10. Has an active infection requiring systemic therapy.
11. Evidence or history of bleeding diathesis or coagulopathy
12. Patient with any pulmonary hemorrhage/bleeding event of NCI-CTCAE v5.0 ≥ Grade 2 within 4 weeks before initiating study treatment; any other hemorrhage/bleeding event of NCI-CTCAE v5.0 ≥ Grade 3 within 4 weeks before initiating study treatment.
13. Patient with thrombotic, embolic, venous, or arterial events, such as cerebrovascular accident (including transient ischemic attacks) within 6 months of informed consent.
14. Presence of a non-healing wound, non-healing ulcer, or bone fracture.
15. History of organ allograft (including corneal transplant).
16. Known or suspected allergy or hypersensitivity to any of the study drugs (sorafenib, and or vemurafenib) study drug classes, or excipients of the formulations given during the course of this trial.
17. All patients with known diagnosis of Neurofibromatosis Type 1 or other known RAS-opathies
18. Patients with uncontrolled seizures
19. Treatment with medications that have known risk of QTc interval prolongation or Torsades de Pointe (TdP) within 14 days or 5 half-lives before dose of either drug is given in this study and for the duration of the study. Refer to Appendix E1 for medications with a known risk of TdP.

20. Treatment with a strong or moderate CYP3A inducers (e.g, phenytoin, carbamazepine, phenobarbital, St. John's Wort [*hypericum perforatum*], dexamethasone at a dose of greater than 16 mg daily, or rifampin [rifampicin], and/or rifabutin) or inhibitors within 28 days before dose of either drug is given in this study and for the duration of the study. Refer to Appendix G.
21. Malabsorption or other significant bowel or stomach resections
22. Has a history or current evidence of any condition, therapy, or laboratory abnormality that might confound the results of the trial, interfere with the patient's participation for the full duration of the trial, or is not in the best interest of the patient to participate, in the opinion of the treating investigator.
23. Has known psychiatric or substance abuse disorders that would interfere with cooperation with the requirements of the trial.
24. Inability to comply with the protocol and/or not willing or not available for follow-up assessments required to assess toxicity

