6. STUDY PROCEDURES

6.1. Screening / Baseline Procedures

Assessments performed exclusively to determine eligibility for this study will be done only after obtaining informed consent. Assessments performed for clinical indications (not exclusively to determine study eligibility) may be used for baseline values even if the studies were done before informed consent was obtained.

All screening procedures must be performed within 28 days prior to initiated study treatment unless otherwise stated. The screening procedures include:

- Informed Consent
- Medical History -To include concurrent baseline conditions (using NCI CTCAE, version 5.0), prior cancer therapy (including documentation of prior surgery, adjuvant or neoadjuvant chemotherapy and radiotherapy).
- ECOG Performance Status (Appendix B)
- Review inclusion / exclusion criteria
- Vital Signs (blood pressure, pulse, respiratory rate, and temperature)
- Complete physical examination including height (cm) and weight (kg)
- Concomitant medication notation to include all medications taken in the last 30 days
- Hematology: CBC with differential and platelet count
- Serum chemistries: glucose, creatinine, BUN, total bilirubin, AST, ALT, alkaline phosphatase, albumin, LDH, total protein, and electrolytes (sodium, potassium, chloride, CO₂, magnesium, calcium). In patients with known Gilbert's syndrome, it is recommended to perform a direct bilirubin and indirect bilirubin. Calculate creatinine clearance (the Cockcroft-Gault equation may be used to calculate the creatinine clearance at any of the time points in this protocol)
- Coagulation: PT, INR
- CA19-9 (or CA 125, or CEA if not expressers of CA 19-9)
- Serum pregnancy test for WOCBP within 72 hours prior to the first dose of study treatment.
- Electrocardiogram (ECG)
- Computed tomography (CT) / magnetic resonance imaging (MRI) scan to document disease status (including chest, abdomen, pelvis, and other regions as clinically indicated. In addition, brain scan is required to exclude brain metastases if clinically indicated only. If a CT scan was taken within 28 days prior to first dose, a new scan is not necessary. (RECIST 1.1 criteria Section 7.1)
- Blood for correlative analysis - 3 X 10 mL

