6.3. Procedures During Treatment (Cycle is 28 Days)

Patients must begin Cycle 1 within 28 days of signing the informed consent document and after the screening assessments. All assessments should be performed within 72 hours of each specified time parameter, with the exception of Cycle 1 in which assessments must be conducted within 24 hours (except those noted), or if medical or scheduling conditions require a delay.

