8.3. Adverse Event Reporting

The study period during which AEs and SAEs as described in Section 8.2 where the patient has been exposed to study treatment must be reported. Reporting period begins at the time of initiation of study treatment and ends 30 days following the last administration of study treatment or study discontinuation/termination, whichever is earlier. After this period, investigators should only report SAEs that are attributed to prior study treatment.

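### Exclusion 2 counts washout from Cycle 1 Day 1 but judges recovery at consent, so up to about 14 days of prior therapy can follow the recovery check

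*Combined protocol and SAP*

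**What the plan says.** Exclusion 2 appears in the synopsis and in Section 4.2, and has two limbs.

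- **Washout**, counted from the start of treatment: "Has had prior chemotherapy, targeted small molecule therapy, or radiation therapy within 2 weeks prior to Cycle 1/Day 1".
- **Recovery**, counted from consent: toxicity must be no worse than "Grade 1 at the time of signing informed consent) from adverse events due to a previously administered agent(s". Neuropathy and alopecia up to Grade 2 are excepted.

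Section 6.3 sets the interval between the two anchors: "Patients must begin Cycle 1 within 28 days of signing the informed consent document and after the screening assessments".

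Section 6.3.1 and Appendix A list an inclusion/exclusion review on Cycle 1 Day 1. Section 6.1 places the graded history at screening: "To include concurrent baseline conditions (using NCI CTCAE, version 5.0), prior cancer therapy". Section 8.3 then opens adverse event collection at dosing: "Reporting period begins at the time of initiation of study treatment".

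Exclusion 8d times two of its cardiac limbs differently again: "new-onset angina within 3 months before randomization, or myocardial infarction within 6 months before randomization".

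**The concern.** The recovery clause is meant to ensure that nobody starts the combination while still carrying more than Grade 1 toxicity from earlier treatment. It can do that only if the check comes after the last earlier treatment. Because the limbs of exclusion 2 run on different clocks, the check can come first and the treatment second.

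Two things are at stake. The first is patient safety at the first dose. The second is the secondary safety endpoint. Section 11.3.5 tabulates all adverse events regardless of cause by maximum grade, so carry-over toxicity that is not documented as present before dosing can be counted as arising on study. Attribution would not be easy: Sections 1.3.1 and 1.3.2 list fatigue, rash, nausea and alopecia as common reactions to both drugs.

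**Working it through.** The plan gives no figure for this interval, so there is none to reproduce. The check is calendar arithmetic on the plan's own windows, with Cycle 1 Day 1 as day 0.

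**Inputs**
- Consent: c days before Day 1, with c at most 28 (Section 6.3).
- Latest permitted prior therapy: w days before Day 1. w = 14, or 15 if the fourteenth day itself counts as inside the two weeks (exclusion 2).
- Recovery check: at consent, so also c days before Day 1 (exclusion 2).

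**Formula**

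Days on which prior therapy can follow the check = max(0, c − w).

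| Consent before Day 1 (c) | w = 14 | w = 15 |
|---|---|---|
| 28 days | 28 − 14 = 14 | 28 − 15 = 13 |
| 21 days | 21 − 14 = 7 | 21 − 15 = 6 |
| 14 days or fewer | 0 | 0 |

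The gap closes when consent is 14 days or less before dosing.

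**Is the check repeated later?** No section requires prior therapy to have ended before consent, and none requires the grade to be judged again after the last prior dose. The Day 1 review applies exclusion 2 as worded, and its recovery limb still refers back to consent.

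**Which anchor do neighbouring criteria use?**

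| Section 4.2 item | Anchor |
|---|---|
| 1, investigational agents | first dose |
| 2, washout limb | Cycle 1 Day 1 |
| 2, recovery limb | consent |
| 4, recovery from major surgery | start of therapy |
| 12, bleeding | start of study treatment |
| 8d, two timed limbs | randomization |

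Exclusion 4 is the closest comparison: it also concerns recovery, and it looks to the start of therapy. The 8d anchor does not exist here, since Section 11.1 describes a single-arm trial.

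**Weight of one patient.** Section 11.2 foresees up to 24 enrolled and at most 12 evaluable. One misclassified patient moves an incidence by 1/24 = 4.2% or 1/12 = 8.3%. This shows sensitivity only; it is not an estimate of how many patients are affected.

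**The case against.** The strongest reply is that the plan has other safeguards, and much of that stands. Appendix A requires the directed examination, vital signs, ECOG status, blood count and chemistries less than 24 hours before first treatment. The Day 1 review covers every criterion, including performance status, organ function and active infection, and exclusion 22 lets the investigator keep out a patient with a current confounding condition. These narrow the gap. They do not close it, because none restates the Grade 1 requirement and exclusion 22 is a matter of opinion rather than a threshold.

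The scenario may also be uncommon. Patients must already have progressed on at least two regimens, so chemotherapy between consent and dosing may be rare. Palliative radiation is more plausible: Section 5.4 allows it even on study, and Section 9.1 warns of radiation sensitization and recall.

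Several stronger conclusions are tempting but not supported:

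- *A reader might infer that carry-over toxicity has no pre-dose record.* The Day 1 tests provide one for laboratory, vital-sign and examination findings, and Section 8.5.2.4 treats conditions present at study start as history. What is missing is a scheduled pre-dose update of graded baseline conditions. Adverse events are assessed on Day 1, but that row of Appendix A does not carry the pre-dose footnote.
- *A reader might infer that carry-over toxicity would by itself trigger dose holds.* Sections 5.3 and 5.3.1 tie modification to drug-related toxicity, so it would also have to be misattributed.
- *A reader might link this to the 53% to 80% exposure in Section 1.4.* The holds there were for rash and hypertension, and nothing connects them with prior therapy.
- *A reader might think exclusion 13 has the same fault*, being timed "such as cerebrovascular accident (including transient ischemic attacks) within 6 months of informed consent". Consent is a definable anchor, and exclusion 5 itself equates study entry with the consent signature. Timing the look-back from first dose would shorten its reach by up to 28 days and admit some patients now excluded.

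**Conclusion.** The point holds as a wording defect with a real but unquantified consequence. As written, up to about 14 days of prior therapy (13 on the stricter count) can follow the only Grade 1 recovery check. A patient with unresolved toxicity from that therapy satisfies both limbs of exclusion 2.

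This rests on two facts of the text: the 28-day maximum from consent to Cycle 1, and the absence of any rule that prior therapy must end before consent. For a patient to be affected, three things must coincide: consent more than 14 days before dosing, further therapy after consent, and unresolved toxicity not caught on Day 1. The documents give no frequency for any of these.

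The two-stage design figures in Section 11.2 are untouched. The undefined anchor in exclusion 8d is minor: it concerns only the two timed limbs, the unstable-angina limb carries no time limit, and exclusion 8b separately bars active coronary artery disease.

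**What to change.** 1. In the synopsis and Section 4.2, reconcile the two anchors in exclusion 2 so that recovery is judged after the last prior therapy, at the Cycle 1 Day 1 eligibility review before the first dose. The washout limb and exclusion 4 already point there. The grade threshold and the neuropathy and alopecia exceptions need not change.
2. In Section 6.3.1 and Appendix A, add a pre-dose Cycle 1 Day 1 entry recording ongoing baseline conditions with their CTCAE grade.
3. In both places where exclusion 8d appears, replace randomization in the two timed limbs with an event that occurs in this trial.

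The cost is a wording amendment and one added record at an existing visit. The downside is that a few patients may fail or be delayed at Day 1. Exclusion 13 needs no change on this ground.
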